4. ESTIMATED DURATION OF THE STUDY

Study enrollment will occur over approximately a two year period. Completion of the entire protocol, including subject recruitment, study procedure execution, and statistical analysis is anticipated to take no longer than four years.

Each subject will be enrolled for a 7 week period, including a screening phase. Study procedures involve weekly clinic visits as an outpatient. Approximately 72 patients will be randomly assigned to either 84 IU of oxytocin (equivalent to 42 IU BID), 168 IU of oxytocin (84 IU BID) or vehicle placebo. The doses of oxytocin are based upon previous studies in humans showing improvement in schizophrenia related changes in behavior and brain function (Kosfeld et al, 2005; Kirsch 2005; Heinrich M 2003).

The total study duration for each individual subject will be approximately 7 weeks, which includes a 7-day screening period, a baseline (randomization) visit, and the six-week treatment phase.

Participants will remain on their current antipsychotic medication and dose throughout the study.

5. LAY LANGUAGE SUMMARY OR SYNOPSIS (no more than one paragraph)

The purpose of this study is to test whether or not people with schizophrenia feel improvement in their symptoms when oxytocin nasal spray is added to their current medications. Volunteers will be randomly assigned to one of three groups; a higher dose group, a lower dose group, or a group who receives a nasal spray with no medication in it (placebo). Volunteers will be asked questions about their mental and physical health as well as take several computer tests to track any changes over the 7 weeks of the study.

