9. RESEARCH DESIGN AND METHODS

OVERVIEW:

The proposed study is a randomized, double-blind, placebo-controlled study of the value of adjunctive intranasal oxytocin added to existing antipsychotic treatment compared with adjunctive placebo in subjects with schizophrenia. Enrolled subjects will be randomized and receive 6 weeks of treatment with one of the following adjunctives to a stable antipsychotic regimen: 1) intranasal oxytocin (84 IU/day), intranasal oxytocin (168 IU/day) or intranasal placebo. The study will be conducted over 2 years. Approximately seventy-one subjects will be entered into the study, on average 35/36 at each site each year.

PRIMARY OUTCOME MEASURE:

Positive and Negative Syndrome Scale (PANSS): The three subscales of the PANSS include the Positive scale (7 items), the Negative scale (7 items), and the General Psychopathology scale (16 items). The total PANSS score is the sum of all 30 items of which each item is scored on a 1-7 rating system (7 indicating the worst symptoms). The items on the PANSS focus on symptoms that are common in patients with psychotic disorders and include hallucinations, delusions and disorganization as well as mood disturbances.

SECONDARY OUTCOME MEASURES WILL INCLUDE:

Global Assessment of Functioning (GAF): The GAF considers psychological, social, and occupational functioning on a hypothetical continuum of mental health illness. Scores on the GAF range from 1 (extremely severe) to 100 (superior functioning).

Clinical Global Impression-Severity of Illness (CGI-S): The CGI-S is used to evaluate changes in overall severity of illness. Scores range from 1 (not at all) to 7 (among the most extremely ill).

Clinical Global Impression-Global Improvement (CGI-I): The CGI-I is a global assessment to evaluate the subject's improvement or worsening from baseline. Scores on the CGI-I scale range from 1 (very much improved) to 7 (very much worse)

Calgary Depression Scale for Schizophrenia (CDSS) is a ten item diagnostic questionnaire intended to assess the severity of depression symptoms experienced by a given patient. The CDSS will be administered by a trained and qualified rater at each scheduled study visit.

Hamilton-Anxiety Scale (HAM-A): The HAM-A is a clinician administered scale for the evaluation of anxiety symptoms. The HAM-A consists of 14 items of which each item is scored 0 (not present) to 4 (very severe).

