- Complete a test on ability to recognize emotions called the Penn Emotion Recognition Test (ER-40) both pre and post in-office dose.
- Will be randomized to Group 1, 2, or 3 (described above) to receive either 84IU, 168IU of oxytocin or placebo
- Fill out questionnaires about mood at the time, experience with close relationships, and symptoms of paranoia both before and at least 50 minutes after the in-office dose of the study drug or placebo.
- Complete a questionnaire about sexual functioning
- The volunteer will be asked to stay at the clinic for one hour after taking the study drug so that the study doctor and study staff can monitor the first experience with the study drug. The study staff will ask questions about how the study drug affects the individual.
- When the study doctor decides the volunteer is ready to go, study drug will be dispensed along with written instructions on how and when to take the study drug.
- Have a blood and saliva sample taken at the beginning of the visit as well as 30 minutes after the in-office dose for monitoring of study drug levels within the body.

Mid-Week Call to Study Site (Day 3 or 4)

The volunteer will be instructed to contact study staff on day 3 or day 4 of taking study drug or the study staff will attempt to contact the volunteer. This information is also on the diary card. We will ask if the volunteer has had any unusual experiences since starting the study drug and if s/he has taken any medications other than the study drug and antipsychotic medication.

Visits 3-8 (weeks 1-6); (approximately 2-3 hours);

During Visits 3-8 of the study the volunteer will:

- Have weight, pulse and blood pressure measured
- Be asked questions about health and any current illnesses or medications (including over-the-counter medications, herbal remedies, alcohol consumption, and substances of abuse).
- Be asked a series of questions about how the volunteer is feeling within the past few weeks such as whether s/he has had anxious feelings, feelings of depression or difficulty concentrating. The staff will also

ask about symptoms that are commonly associated with schizophrenia using a clinical interview called the SCI-PANSS (Structured Clinical Interview – Positive and Negative Syndrome Scale)

- Study drug dispensed along with written instructions on how and when to take the study drug (except at Visit 8)
- Be asked a series of questions inquiring into any occurrences or events of note

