- Complete a questionnaire about symptoms of paranoia and sexual functioning
- Complete a test onability to recognize emotions called the Penn Emotion Recognition Test (ER-40).

Additionally at Visit 8 (week 6 or Early Termination);

- Complete a series of activities which will be used to measure process of thought called the CMINDS® and MSCEIT™ ME
- Have an additional blood sample taken (about 1 tablespoon) to monitor study drug levels in the blood
- EEG paradigm will be conducted

Follow Up Call

The volunteer will be asked to contact the study site one week after the last study drug dose to report taking any new medications or any unusual experiences since stopping the study drug.

Administration and dispensing of the study medication:

Except the one time challenge dose, this is a double-blind study, participants will be randomized to receive one of three possible intranasal study medications adjunctive to their antipsychotics: oxytocin 84 IU, oxytocin 168 IU or placebo (vehicle without oxytocin). Randomization will be performed stratifying gender groups, type of antipsychotic (typical versus atypical) and severity of symptoms based upon PANSS score (<90 versus >90) so that gender, symptom severity and antipsychotic type are distributed relatively evenly across treatment groups. Bottles containing placebo or two different concentrations of oxytocin will be formulated (See Study Drug Formulation below) so that the concentration of oxytocin in the high dose (168 IU) will be double that of the low dose (84 IU). All subjects will be instructed to spray 7 pumps of the spray bottle (one in each nostril, alternating nostrils) to achieve correct dose in the morning and again in the afternoon. Subjects will be given enough study drug at the time of the visit to last until the next visit with extra to cover approximately three additional days. Each pump bottle has 5 ml (300 IU) which is enough for 2.5 days of study drug. Therefore, subjects will be given one spray bottle supply at the time of each visit. The weight of each bottle will be recorded prior to dispensing. After all procedures are performed on baseline visit and study drug is randomly assigned, a dose of the study drug will be taken at the study site, in the presence of a staff member to insure correct administration.

Study Drug Compliance

- 1. Subjects will be instructed on proper use of the nasal device from study staff.

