Analysis Methods: The primary population for efficacy analyses includes all randomized subjects based on the intention-to-treat principle. The population for safety analyses will include all subjects who receive at least one dose of study medication. In the primary analysis, we test the hypothesis of difference in PANSS total change score (Week 6) between the combined oxytocin and placebo groups with adjustment for baseline score using a likelihood-based mixed-effects model for longitudinal data analysis (MMRM LDA) (Fitzmaurice and Ware, 2004). The MMRM LDA model can accommodate incomplete data under the assumption of ignorable attrition (see below under Missing Data). The same MMRM LDA model will be applied to evaluate the dose-response relationship using a linear contrast for the placebo and oxytocin dose groups, comparisons of treatment groups over time using treatment-by-visit (categorical visit variable) interaction term, and the trajectories of treatment responses over time based on time slope computed for each subject (continuous time variable).

Secondary efficacy measures will be the PANSS positive symptom and negative symptom subscales, PANSS general psychopathology subscale, CGI-S, CGI-I HAM-A, CCDS, GAF, cognitive scales as with the primary endpoint using the same MMRM LDA analyses. No multiplicity adjustment will be made in the secondary analyses. Appropriate descriptive statistics with 95% confidence intervals will be provided within and across treatment groups. Normal assumption will be checked and nonparametric alternatives will be considered if the assumption is seriously violated.

Mediators and baseline moderators of treatment effects on efficacy outcome measures will also be explored (Kraemer et al., 2006). The significance of moderator effects due to baseline characteristics (age, gender, initial

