PANSS scores, duration of illness, class of medication) will be tested using treatment-by-baseline characteristic interaction terms in the MMRM LDA and/or ANCOVA models. To assess impact of improvement in one domain (e.g. positive symptoms) on the efficacy of a related symptom domain (e.g. negative symptoms), a mediator analysis model with terms for treatment, baseline, and positive symptoms improvement will be applied to determine significance of oxytocin effect on reductions in negative symptoms after adjustment for potential positive symptom improvement. We will perform similar mediator analysis for assessing inter-relationships between cognitive improvement and symptom improvement in positive and/or negative symptoms. In addition, cross-sectional baseline and longitudinal change score associations between treatment outcome measures and mediator effects will be assessed by including mediators as time-varying covariates in the MMRM LDA models (Diggle et al., 2001).

MU-Suppression. Data will be analyzed in two ways. Pearson rank correlations will be used to examine correlations between mu wave suppression in response to a single dose of OT and symptom severity at the end of 6 weeks of treatment. In additional exploratory analyses, mu suppression values will be split at the median into High suppressors and Low suppressors and followed up by correlations with symptom measures to determine if initial high suppression is correlated with greater improvement in symptom severity. Secondarily, Pearson rank correlations will be conducted between mu wave suppression and symptom severity at baseline, and between mu wave suppression and symptom severity after administration of a single dose of oxytocin.

Safety Endpoints. The safety dataset will contain all subjects who take at least one dose of oxytocin. All adverse events will be coded using the most current version of the Medical Dictionary for Regulatory Activities (MedDRA). The number and percentage of subjects reporting treatment-emergent adverse events will be tabulated within each dose group by treatment, system organ class (SOC) and MedDRA-preferred term. Treatment-emergent adverse events will be those adverse events that begin or worsened following the first dose of study drug. Adverse events will be further classified by severity and investigator-assigned relationship to study drug.

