Clinical laboratory values and vital signs measured at the end of each treatment period will be analyzed using ANOVA, with factors sequence, period and treatment. Dose-response relationships will be explored and any laboratory values that fall outside normal ranges will be identified.

Missing Data. Some observations may be missing after baseline assessment. Individual missing items in all scales will not be imputed. All subjects expressing the desire to discontinue the study will be asked to come in for a final assessment, prior to stopping their medications. The primary analysis will be based on the likelihood based mixed-effects model (MMRM LDA) which provides valid estimates of treatment effect under the missing at random (MAR) assumption. The assumptions about random dropout and MAR can be tested using methods proposed by Diggle et al. (2001) and dropout cohort visualization as in Potkin et al, (2009). Two sensitivity analyses will be conducted to evaluate the robustness of results: one based on a mixed-effects model for missing not at random (MNAR) data with covariate adjustment for dropout measures (Wu and Follmann, 1999; Wu et al., 2001), and the other based on the usual LOCF-ANCOVA method with missing data following dropout imputed by an individual's last observed measurement. Further details are provided in the Statistical Analysis Plan, which will clearly specify the mixed-effects model methodology, sensitivity analyses, and evaluation of the assumptions.

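### Labs and vital signs are to be analysed with crossover terms in a one-period parallel trial, and two sentences define the safety set in ways that may not agree

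*Combined protocol and SAP*

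**What the plan says.** **Model.** The paragraph that follows Safety Endpoints in Section 9 says that labs and vital signs "measured at the end of each treatment period will be analyzed using ANOVA, with factors sequence, period and treatment". Its next sentence adds an exploration of dose-response and the flagging of out-of-range values, and names no model for either.

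**Design.** Section 4 describes "a 7-day screening period, a baseline (randomization) visit, and the six-week treatment phase". The Section 9 Overview says "Enrolled subjects will be randomized and receive 6 weeks of treatment with one of the following adjunctives". Footnote h to the visit schedule calls the design parallel-group. No sequence, second period or washout is defined.

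**Safety set.** Analysis Methods says: "The population for safety analyses will include all subjects who receive at least one dose of study medication". Safety Endpoints says: "The safety dataset will contain all subjects who take at least one dose of oxytocin". Placebo is a study medication, because the section on administration and dispensing lists "one of three possible intranasal study medications adjunctive to their antipsychotics: oxytocin 84 IU, oxytocin 168 IU or placebo".

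**Challenge dose.** Footnote k gives every subject an oxytocin challenge between the screening EEG recordings, while the mu wave paragraph presents the EEG work as a sub-study that needs the subject's agreement. The challenge stands apart from assigned treatment: "Except the one time challenge dose, this is a double-blind study". At Baseline, subjects stay in clinic so that staff can "monitor the first experience with the study drug".

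**The concern.** Sequence and period belong to a crossover analysis, and this trial gives them nothing to estimate. As far as the text goes, the only named model for labs and vital signs does not match the design, so any analyst must depart from it. If that choice is left until the data are in hand, it becomes a post hoc decision.

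The two safety-set sentences matter because adverse events are to be reported as numbers and percentages by treatment. If the set is built on exposure to oxytocin, the placebo denominator depends on who took the challenge and on whether it counts.

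Safety and tolerability of the two doses are stated aims (Specific Aims 2 and 5). Section 15 says that blood chemistry and urine osmolality are there to monitor for SIADH. The between-arm laboratory comparison is therefore a main quantitative safety output.

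**Working it through.** The plan gives no figure to reproduce here. The check is structural, followed by a head count.

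**Inputs.** Three arms of 24 (Sample Size Calculation, N = 72) and one treatment phase (Section 4). Totals of 71 and 80 also appear in the document; the structural result does not depend on which applies.

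**Degrees of freedom for treatment.** This is the rank of the model with treatment minus the rank without it.

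| How the terms are read | Rank without treatment | Rank with treatment | Treatment df |
|---|---|---|---|
| Period constant, sequence = arm | 3 | 3 | 0 |
| Period constant, sequence with one level | 1 | 3 | 2 |
| Six weekly visits as periods, sequence = arm | 1 + 2 + 5 = 8 | 8 | 0 |
| Sequence and period deleted | 1 | 3 | 2 |

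In the first and third rows sequence is fully aliased with treatment. In the second, both extra terms are empty. On no reading do they do any work beyond what arm and visit would do under their own names.

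**Safety-set size.** Assume that all 72 randomised subjects are dosed.

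- Analysis Methods wording: 24 + 48 = 72.
- Safety Endpoints wording: 48 + 24u + m. Here u is the fraction of the placebo arm whose challenge was taken and counts, and m is the number of people challenged but never randomised. Neither is stated, so u is shown over its full range and m is left open.

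| u | Randomised subjects in the set | Placebo subjects left out |
|---|---|---|
| 0 | 48 + 0 = 48 | 24 |
| 0.5 | 48 + 12 = 60 | 12 |
| 1 | 48 + 24 = 72 | 0 |

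Any m above 0 adds people who belong to no arm, so at u = 1 the set would exceed 72.

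**Time points for the model.** The visit schedule puts blood chemistry and urine osmolality at screening and Visit 8/early termination, which is 2 occasions. Section 15 puts them at screening and every visit after randomisation: 1 + 6 = 7, or 8 if Baseline is counted. Section 14 says that blood is drawn 8 times for the chemistry panel. Vital signs are scheduled at screening, Baseline and each weekly visit. Replacing the period wording with actual time points therefore requires the lab schedule to be settled first.

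**The case against.** The strongest reply is that nothing is really lost. The documents define no sequence, so 0 df is conditional on coding it as the arm. Even with that coding, the same 2-df three-arm comparison appears under the label of sequence. That is correct. A reader might infer that the trial cannot compare labs or vital signs between arms; the documents do not support that. What stands is narrower: the model as worded does not fit the design and needs repair.

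It might also be said that details are deferred to a separate analysis plan. The Missing Data paragraph does defer some, but for the mixed model, the sensitivity analyses and their assumptions. It does not mention the safety model.

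On the safety set, footnote k says that all subjects receive the challenge, which gives u = 1 and loses no randomised placebo subject. The tabulation by treatment also suggests that placebo was meant to be included. A reader might infer that the plan drops placebo from the safety analysis; the text supports only that the denominator may differ. The optional EEG wording and the separation of the challenge from assigned treatment keep u below 1 possible.

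A further tempting inference is that adverse events between the challenge and Baseline go unrecorded, because the adverse-event row of the schedule begins at Baseline. Section 15 says that subjects are monitored throughout the study, and the schedule footnotes allow screening and Baseline on one day. Neither settles the matter, but a gap is not established.

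Carry-over from the earlier proof-of-concept study, which was a crossover (Specific Aim 1), is a plausible explanation. Section 15 also speaks of two baseline visits. The documents do not state the origin of the wording.

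**Conclusion.** Two points hold with high confidence. The lab and vital-sign model is wrong as written for a one-period, three-arm parallel trial: period is constant, and sequence is either aliased with treatment (0 df) or empty. The two safety-set sentences also conflict in wording. The number of placebo subjects left out ranges from 0, if all take the challenge and it counts, to 24, if it does not count. People never randomised could be added on a literal reading. That range rests on 24 per arm, all dosed, with u and m unstated.

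The reach is limited to secondary safety reporting. The primary PANSS comparison, its alpha and its power do not depend on either passage, and the flagging of out-of-range values can proceed regardless. This should be fixed because the repair is cheap and safety is a stated aim, but it is at the lower end of that grade.

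**What to change.** 1. **Lab and vital-sign model.** Delete sequence and period, and replace the reference to ends of treatment periods with named visits. Compare the three arms by ANCOVA on the Week 6/early-termination value, adjusted for the pre-treatment value. For weekly vital signs use a repeated-measures model by visit.
2. **Lab timing.** Reconcile the visit schedule, Section 14 and Section 15, so that the values entering the model are known.
3. **Safety set.** Use one definition: all randomised subjects who took at least one dose of assigned study medication, placebo included, tabulated by arm. This keeps the sense of the Analysis Methods sentence and adds randomisation and assignment explicitly. Delete the competing sentence in Safety Endpoints.
4. **Challenge interval.** List separately any events after the challenge and before the first assigned dose. Confirm that they are recorded. As a clarification only, state that the treatment-emergent window opens at the first assigned dose.

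The sponsor must also reconcile the challenge-dose wording (mu wave paragraph, footnote k and the Visit 1 list), but that is a separate matter.

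The cost is a few sentences, one schedule reconciliation and one extra listing. New data collection arises only if events between the challenge and Baseline are not already captured.

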Specific Aim #3:Establish the time needed to reach peak efficacy. Duration of treatment in the original study was three weeks, and significant therapeutic benefit was observed only at the three-week endpoint but not earlier. In the proposed study, subjects will receive study drug for 6 weeks and we expect that the size of the therapeutic benefit of oxytocin will increase from 3 to 6 weeks.

Specific Aim # 4: Investigate the possible cognitive effects of intranasal oxytocin. In the pilot study, oxytocin significantly improved short term recall performance in the California Verbal Learning Test. This raises the possibility that chronic oxytocin will improve cognitive deficits associated with schizophrenia. This study will test this hypothesis using the Computerized Multiphasic Interactive Neurocognitive DualDisplay™ System (CMINDS®) and Mayer-Salovey-Caruso Emotional Intelligence Test: Managing Emotions (MSCEIT™ ME).

Specific Aim #5: To determine if daily intranasal oxytocin is sufficiently safe, feasible and acceptable to patients to warrant further clinical development. Information derived from this study will inform development of oxytocin not only for schizophrenia but other potential neuropsychiatric disorders.

Specific Aim #6: The objective of the study is to compare the efficacy of intranasal oxytocin versus intranasal placebo to improve symptoms in schizophrenia patients who have residual symptoms despite being on adequate treatment with antipsychotic medication. Improvement will be measured by total score in the Positive and Negative Syndrome Scale (PANSS).

Specific Aim #7: To determine if oxytocin-induced enhancement of mu-rhythm suppression of 'mirror' neurons in schizophrenia patients can serve as a predictive biomarker of individual clinical response to this neurohormone.

Secondary objectives include:

 To evaluate the efficacy of intranasal Oxytocin as measured by change in the total CGI-Severity and Improvement scores

- To evaluate the efficacy of intranasal Oxytocin as measured by change in the total GAF score
- To evaluate the efficacy of intranasal Oxytocin as measured by change in the total scores of HAM-A.
- To evaluate the efficacy of intranasal Oxytocin on self-rated social anxiety as measured by change in the total Social Phobia Inventory (SPIN).
- To evaluate the efficacy of intranasal Oxytocin as measured by change in the total Calgary Depression Scale for Schizophrenia (CDSS) scores.

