15. RISK MANAGEMENT PROCEDURES AND ADEQUACY OF RESOURCES

A staff that is highly qualified in the assessment and treatment of schizophrenia in adults will closely monitor subjects in this study. This monitoring includes the frequent periodic assessments involved in the study protocol, which occur at intervals of 1 week long. Study drug will be administered on site following both baseline visits. Mid-week calls are set up following both baseline visits along with a study treatment follow up visit. In addition, subjects will be monitored throughout the study for any adverse events. Subjects will be instructed by the Investigator to report the occurrence of any adverse events immediately. At the beginning of each treatment period, the Investigator will query the subjects, in a generalized fashion, whether any clinical adverse events have occurred since the last visit. Any serious or unexpected event, including death due to any cause, whether or not related to the study drug or procedures, will be reported to the UCSD HRPP within 10 days.

After a thorough literature search was performed and confirmed the relative safety profile of this drug, the following additional safety measures were added in an attempt to be thorough.

Biological safety measures include blood chemistry and urine osmolality to monitor for SIADH. These tests will be done at screening and at every visit after randomization. In addition a blood metabolic assay (glucose, liver enzymes) will be conducted at each visit.

If any clinical worsening or serious adverse event is detected during the course of the trial that cannot be managed by a dose adjustment, the subjects will be discontinued from the protocol.

It is my intention to provide contact information for study staff to the subjects and reiterate this information at the time of each visit. Contact information for PI, and Drs. [name] and [name], are listed on the diary form that will be provided to the subject at each visit. Study subjects will be encouraged, as documented in the consent and on the separate diary form, to contact the study team with medical concerns, reactions, and experiences. Subjects will be given a diary form to complete upon each use for administrations that are done between site visits. This diary form includes 24 hour emergency contact information (including PI, sub-Is and study staff), nearest emergency department from subject's residence and concomitant medication diary.

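### The plan treats MAR as testable and counts LOCF-ANCOVA as a robustness check, but observed data cannot separate MAR from MNAR and LOCF's no-change assumption conflicts with Aim 3

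*Combined protocol and SAP*

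**What the plan says.** All of the following is in Section 9 of the protocol unless stated.

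- **Primary contrast (Analysis Methods).** "we test the hypothesis of difference in PANSS total change score (Week 6) between the combined oxytocin and placebo groups", adjusted for baseline, in all randomized subjects. On incomplete data: "The MMRM LDA model can accommodate incomplete data under the assumption of ignorable attrition".
- **Assumption (Missing Data).** The primary analysis is a likelihood-based mixed model "which provides valid estimates of treatment effect under the missing at random (MAR) assumption".
- **Testability (Missing Data).** "The assumptions about random dropout and MAR can be tested using methods proposed by" a cited text on longitudinal data, supported by plots of dropout cohorts.
- **Sensitivity analyses (Missing Data).** "Two sensitivity analyses will be conducted to evaluate the robustness of results". The first is a mixed-effects model for MNAR data that adjusts for dropout measures. The second is "the usual LOCF-ANCOVA method with missing data following dropout imputed by an" individual's last measurement.
- **Expected course (Section 6, Aim 3).** "we expect that the size of the therapeutic benefit of oxytocin will increase from 3 to 6 weeks". The same aim reports that in the earlier three-week study significant benefit appeared only at the last time point.
- **Route to dropout (Section 15).** "If any clinical worsening or serious adverse event is detected" and adjusting the dose does not deal with it, the subject leaves the protocol.

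Subjects who wish to stop are asked to attend a final assessment, and the visit schedule has PANSS at every weekly visit and at early termination. Details of the models, sensitivity analyses and checks of assumptions are deferred to a Statistical Analysis Plan, and no separate text of it is among the documents available. The documents give no dropout rate, no range of departures from MAR, and no rule for reading agreement or disagreement between analyses.

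**The concern.** The sentence on testing joins two different claims. Whether dropout is completely random or related to recorded history can be examined in the data, so that half is defensible. Whether dropout also depends on values never recorded cannot be examined. A non-significant test of MAR would invite a conclusion that it cannot carry, and the primary analysis rests on that assumption.

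LOCF-ANCOVA adds little to the check. It replaces one assumption with another (no change after the last rating), and that assumption contradicts what the trial expects. A gap between LOCF and the MMRM may only reflect frozen early scores, and agreement between them says nothing about the unseen Week 6 values. The MNAR model is then the only informative sensitivity analysis, and no graded range of departures shows how far from MAR the conclusion survives.

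**Working it through.** The plan gives no figure of its own on dropout or on the size of a departure from MAR, so there is none to reproduce. Dropout shares and benefit paths below are assumptions. The design figures (24 placebo, 48 oxytocin, six ratings, AR(1) correlation 0.5, effect 0.3 SD) come from the sample size paragraph of Section 9.

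**1. What observed data can distinguish.** One trial was simulated with 24/48 subjects, six visits and AR(1) 0.5; 5 of 48 oxytocin subjects dropped out (10.4%). Only the unseen post-dropout oxytocin values were then shifted upward (worse) by δ. The entries are oxytocin minus placebo at Week 6, in SD.

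| δ (SD) | MMRM-type estimate | LOCF difference | Difference with complete data |
|---|---|---|---|
| 0 | −0.361 | −0.430 | −0.290 |
| 0.5 | −0.361 | −0.430 | −0.238 |
| 1 | −0.361 | −0.430 | −0.186 |
| 2 | −0.361 | −0.430 | −0.082 |

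The last column moves by (5/48) × δ; for δ = 1, −0.290 + 0.104 = −0.186. The recorded data are identical in all four rows, so no test or plot of them can tell the rows apart, and LOCF cannot respond to the difference.

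**2. What LOCF does when dropout is completely random.** Let a share f drop out in each arm, with the last rating spread evenly over Weeks 1 to 5 and the same timing in both arms, so that the placebo course cancels. Let r be the mean fraction of the Week 6 benefit already present at those visits.

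LOCF effect ÷ true Week 6 effect = (1 − f) + f × r = 1 − f(1 − r)

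- *Late path*, fractions 0, 0, 0.50, 0.667, 0.833: r = 2.00/5 = 0.40, so the loss is 0.60f.
- *Linear path*, fractions 1/6, 2/6, 3/6, 4/6, 5/6: r = 2.5/5 = 0.50, so the loss is 0.50f.

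| f | Loss, linear path | Loss, late path |
|---|---|---|
| 10% | 5% | 6% |
| 20% | 10% | 12% |
| 30% | 15% | 18% |

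MAR holds in every cell, so a gap between LOCF and the MMRM would not be evidence against MAR.

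**3. What a graded check would report.** Suppose oxytocin dropouts are worse than MAR predicts by δ and placebo dropouts are as predicted. The Week 6 contrast then moves by f × δ. Taking 0.3 SD as the Week 6 effect (an assumption, because the plan states it as time-averaged), the δ that erases it is 0.3/f: 3.0, 1.5 and 1.0 SD at 10, 20 and 30% dropout. A tipping-point analysis supplies a statement of this kind; LOCF does not.

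**The case against.** The strongest reply is that the plan already departs from MAR. Its first sensitivity analysis is an explicit MNAR model, and no rule says that agreement proves anything. This stands. A reader might infer that the plan would certify its primary result on an empty test plus LOCF alone, but the documents do not support that.

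A reader might also infer from Section 15 that withdrawal for worsening makes the data MNAR. It does not. Dropout that depends on recorded worsening is MAR, and the weekly PANSS, the early-termination PANSS and the requested final assessment all help to record it. They make MAR more plausible, but they do not supply the later Week 6 value or make MAR verifiable.

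It is tempting, too, to read Aim 3 as saying that the earlier study found no benefit before three weeks. It says no *significant* benefit, which in a small crossover study is not zero. Hence the linear path is shown beside the late one.

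On size, LOCF attenuates the effect in these scenarios, so it is conservative there. Against 0.3 SD, a 5-18% loss is 0.015-0.054 SD, while the unadjusted Week 6 standard error is √(1/24 + 1/48) = 0.25 SD, so the loss is 0.06-0.22 standard errors. That is modest for a pilot of this size. The issue is what LOCF can be taken to show, more than the bias itself.

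LOCF can even do better than the MMRM. In simulations with no true effect, flat average courses and oxytocin dropout driven by unseen bad scores (about 15, 28 and 42% oxytocin dropout), the mean LOCF estimates were 0.004, 0.019 and 0.010 SD, against −0.062, −0.099 and −0.155 for the MMRM-type model. But average scores there do not change over time, which is the condition that Aim 3 expects not to hold.

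**Conclusion.** The point holds in a limited form. The statement that MAR can be tested is wrong as to MAR versus MNAR. LOCF-ANCOVA is a poor choice for one of only two robustness analyses, because its assumption conflicts with Aim 3 and it cannot respond to unseen values. The primary MMRM is not at fault, and the plan does contain an analysis that departs from MAR.

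The illustrated LOCF loss of 5-6/10-12/15-18% rests on assumed dropout of 10/20/30%, equal in share and timing across arms, and on assumed benefit paths. With no stated rate, the actual size cannot be fixed.

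A reader might go further and say that the MNAR model gives the wrong effect because dropout occurs after randomization. That would follow only if its treatment coefficient were read at a fixed dropout level. The protocol does not say how the effect will be summarised and defers the detail, so this is a matter to specify and not an established error.

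**What to change.** 1. **Reword the testability sentence.** Say that completely random dropout will be assessed against recorded history, and that MAR cannot be verified and will be stressed by sensitivity analysis.
2. **Keep the MNAR model and specify its summary.** State that the treatment effect is averaged over each arm's own dropout distribution: with p the share and μ the modelled Week 6 mean in dropout group k, report Σ p(oxytocin, k) μ(oxytocin, k) − Σ p(placebo, k) μ(placebo, k).
3. **Replace LOCF-ANCOVA as a robustness analysis.** Use multiple imputation consistent with the MMRM (same baseline adjustment, treatment-by-visit means and covariance), then add δ to the imputed values of oxytocin dropouts. Fix the δ range in PANSS points before the unblinded interim look, and report where the conclusion changes. Reference-based imputation toward the placebo course is optional, since it sets a particular post-dropout course and does not simply test MAR.
4. **Keep LOCF at most as a descriptive table**, with a note that it is not evidence for or against MAR.

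The cost is SAP wording, standard imputation code and some added analysis work. No new data and no extra burden on subjects are needed. The drawback is less direct comparability with older trials analysed by LOCF, which the descriptive table partly offsets.
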